### 6.1.2. Exclusion Criteria

Ocular specific exclusion criteria apply to the **study eye** only, unless otherwise specified.

1. GA secondary to a condition other than AMD such as Stargardt disease, cone rod dystrophy, or toxic maculopathies like plaquenil maculopathy in either eye.
2. Spherical equivalent of the refractive error demonstrating >6 diopters of myopia or an axial length >26 mm.
3. Any history or active CNV, associated with AMD or any other cause, including any evidence of RPE tears or evidence of neovascularization anywhere based on SD-OCT imaging and/or FA as assessed by the reading center.
4. Presence of an active ocular disease that in the opinion of the investigator compromises or confounds visual function, including but not limited to, uveitis, other macular diseases (eg, clinically significant epiretinal membrane, full thickness macular hole or uncontrolled glaucoma/ocular hypertension). Benign conditions in the opinion of the investigator such as peripheral retina dystrophy are not exclusionary.
5. Intraocular surgery (including lens replacement surgery) within 3 months prior to randomization.
6. History of laser therapy in the macular region.
7. Aphakia or absence of the posterior capsule. Note: Yttrium aluminum garnet laser posterior capsulotomy for posterior capsule opacification done at least 60 days prior to screening is not exclusionary.
8. Any ocular condition other than GA secondary to AMD that may require surgery or medical intervention during the study period or, in the opinion of the investigator, could compromise visual function during the study period.
9. Any contraindication to IVT injection including current ocular or periocular infection.
10. History of prior IVT injection.
11. Prior participation in another interventional clinical study for IVT therapies in either eye (including subjects receiving sham).
12. Prior participation in another interventional clinical study for GA in either eye including investigational oral medication and placebo.
13. Participation in any systemic experimental treatment or any other systemic investigational new drug including within 6 weeks or 5 half-lives of the active ingredient (whichever is longer) prior to the start of study treatment. Note: clinical trials solely involving observation, over-the-counter vitamins, supplements, or diets are not exclusionary.

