### **8.1.1. Screening Period—Within 28 Days Prior to Randomization/Treatment (Day –28 to Day –1)**

#### **8.1.1.1. Visit 1—All Subjects**

Note: All ophthalmic procedures (including imaging) are to be performed on both eyes, except where specified.

Before any study-specific procedures are performed, the purpose and nature of the study should be explained and the patient should read, sign, and date the institutional review board/independent ethics committee (IRB/IEC)–approved informed consent form (ICF). The individual obtaining consent from the patient and a witness, if applicable, should also sign and date the ICF. Once the patient has signed the ICF, a screening number should be assigned to the patient. Demographic information, significant medical/surgical history within the previous 5 years, invasive ocular procedures within the previous 5 years, and concomitant medications used within 30 days prior to screening should be collected (including vitamins and all over-the-counter as well as prescription medications). Complete smoking/tobacco history should also be collected.

Subject eligibility should then be determined by reviewing the inclusion/exclusion criteria and the study eye should be selected. Prior to the administration of fluorescein, blood and urine should be collected for safety labs (including blood for human chorionic gonadotropin/follicle-stimulating hormone/luteinizing hormone, if applicable) and vital signs along with a physical examination including weight and height should be performed.

A complete ophthalmic exam including slitlamp exam of the cornea, iris, anterior chamber, aqueous reaction (cells and flare), dilated fundus exam of the vitreous and retina, and IOP measurement. Normal luminance best corrected visual acuity should be performed prior to dilating the eyes. Images should be captured as outlined in the Visit Schedule (FAF, NIR, digital color fundus photography, fundus fluorescein angiography [FFA]) and forwarded to the reading center for determination of eligibility if applicable.

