### **9.2. Demographic Information/Medical/Surgical History**

Demographic information will be collected from all subjects including but not limited to date of birth, race/ethnicity (where locally permitted). All significant medical conditions and surgeries within the past 5 years should be captured for the subject including chronic and ongoing conditions. Any history or current use of tobacco is to be collected.

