### **9.3. Ocular History/Ocular Procedures**

Ocular history within the previous 5 years should be collected and recorded for all subjects. The history should include any significant previous ocular surgeries, procedures and/or medications or treatments used for these conditions.

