- NL-BCVA (< 60 vs. ≥ 60 ETDRS letters) and LLD (< 20 vs. ≥ 20 ETDRS letters) combinations
- Advanced AMD (fellow eye with: GA only, GA with CNV, CNV only, neither GA nor CNV)
- GA laterality (bilateral GA vs. study eye GA Only)
- Presence of CNV in fellow eye (as randomized and actual status (based on medical history))
- Lens status:
 - Phakic
 - Pseudophakic
- Reading speed assessment method

- Monocular and binocular maximum reading speed and critical print size (without adjustment for reading inaccuracy)
- Monocular maximum reading speed categories (<60, 60-<160, ≥160 words per minute (wpm))
- Monocular maximum reading speed categories (approximately tertiles based on APL2-303/304 combined data*) – study eye only
- Mean FRI Index score
- FRI Level (1,2,3,4)
- NEI VFQ-25 distance activity subscale score
- NEI VFQ-25 near activity subscale score
- NEI VFQ-25 driving subscale score
- Number of subjects currently driving at baseline
- NEI VFQ-25 composite score
- C3 Complement level
- C3 Complement level categories (tertiles of C3)
- Dry AMD status (iRORA, large drusen) (at Month 24 reporting only)

*Approximately tertiles will be specified consistently across the APL2-303/304 studies to the nearest clinically relevant level.

Baseline will be defined as the last available pre-treatment value taken on or before the first dose date of study drug. In the case a subject did not receive study drug in the ITT population, the last assessment prior to study exit will be used as baseline.

Conversions for height and BMI are as follows:

- Height (m) = Height (cm) x 0.01
- Body mass index (kg/m²) = Weight (kg) / [Height (m)]²

Demographics and baseline characteristics will also be listed for the ITT set.

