6. EFFICACY ANALYSES

Efficacy analysis including primary, key secondary, secondary, and exploratory analysis will be performed primarily using the mITT set, with subjects grouped according to the treatment assigned at randomization. Available data from all randomized subjects regardless of adherence to the protocol will be included in the efficacy analyses; this includes data from subjects who discontinued study drug early but continued with study assessments. All efficacy data will be listed for the ITT set.

Unless otherwise noted, hypothesis testing and estimation of treatment effects will be performed with a mixed effect model for repeated measure (MMRM) that includes data from all three treatment arms (PM, PEOM, and Sham). The Sham arm will represent the pool of the two sham treatment groups: SM and SEOM (i.e., the two sham arms will be pooled into a single “control” group). All hypothesis tests for efficacy endpoints will be two-sided.

Unless otherwise noted, analysis of efficacy endpoints (primary, key secondary, secondary, and exploratory) in the overall population will be adjusted for the following randomization stratification factors (actual status) and baseline covariates:

For primary efficacy endpoint

- Presence of CNV in the fellow eye (yes; no)
- Baseline GA lesion area ($< 7.5 \text{ mm}^2$ or $\geq 7.5 \text{ mm}^2$)

For key secondary, secondary, and exploratory endpoints

- Presence of CNV in the fellow eye (yes; no)
- Baseline GA lesion area ($< 7.5 \text{ mm}^2$ or $\geq 7.5 \text{ mm}^2$)
- Baseline value of the endpoint

Of note, the randomization stratification factors were assessed at the screening visit. In the event of a change in status in the GA lesion area between the screening visit and the baseline visit (i.e., GA lesion area $< 7.5 \text{ mm}^2$ at screening to $\geq 7.5 \text{ mm}^2$) then the baseline status will be used.

If a statistical model is not directly specified and if necessary, data will be analyzed with the following approaches:

- For continuous endpoints, the MMRM analysis described for the primary endpoint in Section 6.2.2.
- For categorical or ordinal variables, a Cochran Mantel Haenszel (CMH) test with the baseline category status, presence of CNV in the fellow eye (yes or no), and baseline GA lesion area ($< 7.5 \text{ mm}^2$ or $\geq 7.5 \text{ mm}^2$) as stratification factors.

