7.1.1. TEAEs of New Onset Exudative AMD

For subjects who experience a TEAE of “Choroidal neovascularization” or “Neovascular AMD” (“Exudative AMD TEAE”), the following summaries will be performed:

- The overall summary table described in Section 7.1 will be repeated replacing “TEAEs” with “Exudative AMD TEAEs”. This will be reported for the study eye.
- The incidence of Exudative AMD TEAEs in the study eye will be presented by treatment group and overall. In addition, the analysis will be repeated by fellow eye CNV status at baseline and study eye DLS on SD-OCT at baseline. A similar analysis will be repeated for the Exudative AMD TEAEs in the fellow eye with an additional analysis by fellow eye DLS on SD-OCT at baseline. Subjects with a medical history of CNV in the corresponding eye will be excluded from the analysis.
- The incidence and rate per 100 subject-years of Exudative AMD TEAEs in the study and fellow eye as well as a summary (for study and fellow eye) and Kaplan Meier plot for the time to development of Exudative AMD TEAEs in the study eye will be presented by treatment group and overall. Subjects with a medical history of CNV in the corresponding eye will be excluded from the analysis.
- In addition, the characteristics of the Exudative AMD TEAEs in the study eye will be presented at baseline, study visit preceding exudation, study visit at exudation and at Month 12 (or Month 24 if the final analysis) for characteristics based on SD-OCT and baseline, study visit at exudation and at Month 12 (or Month 24 if the final analysis) for characteristics based on Fluorescein Angiography (FA). The following characteristics will be presented by treatment group and overall:

- Presence of cystoid spaces on SD-OCT
 - Central (center point) retinal thickness on SD-OCT
 - Central subfield thickness on SD-OCT
 - Presence of CNV on FA.
 - CNV type on FA
 - Presence of subretinal fluid on SD-OCT
- A summary of concomitant anti-VEGF therapy for new exudative AMD in the study eye will be provided by treatment group and overall. This summary will include the total number of subjects that received any anti-VEGF for new exudative AMD as well as the average number of injections per month post exudative AMD. There will also be a breakdown by preferred term of ranibizumab or aflibercept and the average number of injections per month for each term. Subjects will be presented by the number of injections received for that medication.

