7.7. Other Ophthalmology Imaging Assessments

Unless otherwise stated, ocular imaging data collected will be listed by treatment group and overall for the Safety set. The summary will be performed separately by study eye and by fellow eye. The ophthalmology imaging assessments performed in this study include the following:

- Digital Color Fundus Photographs (DCFP)
 - Shift from baseline in the presence/absence of hemorrhage at each visit
- FA
 - The following analyses will be performed in all study eyes and in non-study eyes without a history of CNV at baseline (in medical history) in the corresponding eye.
 - Incidence of new CNV. This will be summarized as the cumulative number of CNV events by each visit and the cumulative incidence by that visit based on Kaplan Meier methods.
 - Incidence of new CNV by type (classic, occult, classic & occult, disciform scar) at first emergence will be summarized at each visit for the cumulative number of events.
 - Total CNV size (diameter) at first emergence will be summarized at each visit for the cumulative number of events.
- SD-OCT
 - Descriptive statistics on central subfield thickness at each visit
 - Plot of the mean change from baseline in central subfield thickness in the study eye \pm the standard error over time by treatment group.
 - Descriptive statistics on central (center point) retinal thickness at each visit
 - Shift from baseline in the presence/absence of subretinal fluid at each visit
 - Shift from baseline in the presence/absence of cystoid spaces at each visit
- Specular Microscopy

- Endothelial Cell Count is assessed using specular microscopy, and the change from baseline in cell density (cells/mm²) as well as the change from baseline in average cell-size will be summarized with descriptive statistics.
- OCT-A
 - Incidence of subclinical CNV (referred to as MNV in the datasets) determined by OCT-A in eyes without previous CNV reported in the medical history or as an adverse event in the corresponding eye at each visit.

In addition, the following summary of suspected and reading-center confirmed CNV cases will be presented by treatment group. This will be presented separately for the study eye only.

- The number and percentage of subjects with an Exudative AMD TEAE on or before Month 12 (or Month 24 if the final analysis)

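### Baseline fellow-eye CNV status rests on a five-year history alone, so some CNV that is older or first seen at screening may be classed as absent and later counted as new in the fellow eye

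*Protocol*

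**What the plan says.** **Collection.** Protocol 9.3 states: "Ocular history within the previous 5 years should be collected and recorded for all subjects". Section 8.1.1.1 and footnote C of Appendices A to D set the same window for invasive ocular procedures. Footnote C and section 7.5.1 set it for fellow-eye treatment. Section 9.2, on general medical history, is wider: "All significant medical conditions and surgeries within the past 5 years should be captured for the subject including chronic and ongoing conditions". Section 9.3 does not repeat that extension.

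**Use.** SAP 5.2 lists the baseline variable as "Presence of CNV in fellow eye (as randomized and actual status (based on medical history". SAP 6 says that the efficacy analyses are "adjusted for the following randomization stratification factors (actual status) and baseline covariates", and fellow-eye CNV is one of those factors. SAP 6.2.5 uses it as a subgroup, and SAP 7.1.1 splits the incidence of exudative AMD in the study eye by it.

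**At-risk and comparison sets.** For exudative AMD events, SAP 7.1.1 says: "Subjects with a medical history of CNV in the corresponding eye will be excluded from the analysis". For new CNV on FA, SAP 7.7 analyses all study eyes and takes events "in non-study eyes without a history of CNV at baseline (in medical history) in the corresponding eye"; disciform scar is one of the CNV types that it tabulates at first emergence. SAP 6.6.3 requires no CNV in the medical history for fellow eyes in the GA comparison.

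**Imaging.** For the screening visit, Protocol 8.1.1.1 says: "All ophthalmic procedures (including imaging) are to be performed on both eyes, except where specified". Appendices A and C mark FFA and SD-OCT at screening without a study-eye restriction. None of the SAP sections above uses those images to decide whether the fellow eye already has CNV.

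**The concern.** The variable is meant to describe whether the fellow eye has CNV at baseline, but its stated source need not contain all such CNV. Two routes lead to a wrong No:

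- CNV that arose and was last treated more than five years before screening, and that the site did not list as ongoing;
- CNV first seen on the screening FA or SD-OCT and not carried into the history.

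Two outputs are exposed. In the fellow-eye FA table, a lesion that was there from the start can be read as incident at Month 12 or 24, and an old disciform scar has an accepted category to fall into. In the study-eye exudative AMD breakdown, higher-risk subjects move into the group without fellow-eye CNV. That breakdown matters because Protocol 4.1.4 reports that 17 of the 25 pegcetacoplan-treated Phase 2 subjects with new study-eye CNV had neovascular AMD in the fellow eye, and says that such a history may raise the risk.

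**Working it through.** The plan states no figure for this misclassification, so there is none to reproduce. The Phase 2 counts in Protocol 4.1.4 agree with their percentages: 25/165 = 15.2% (given as 15%) and 17/25 = 68%.

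**Inputs.** N = 600 subjects (Protocol synopsis). Two inputs are assumptions, because the documents give neither: p, the share of subjects who truly have fellow-eye CNV, taken as 20–40%; and m, the share of those eyes recorded as No, taken as 0–30%. The range includes m = 0, which applies if sites record all older CNV as chronic or ongoing and screening finds none that is new.

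**Fellow-eye set.** Eyes wrongly recorded as No = 600·p·m. Their share of all eyes recorded as No is c = p·m / (1 − p + p·m).

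| p | m = 0 | m = 10% | m = 20% | m = 30% |
|---|---|---|---|---|
| 20% | 0 eyes, 0% | 12 eyes, 2.4% | 24 eyes, 4.8% | 36 eyes, 7.0% |
| 30% | 0 eyes, 0% | 18 eyes, 4.1% | 36 eyes, 7.9% | 54 eyes, 11.4% |
| 40% | 0 eyes, 0% | 24 eyes, 6.3% | 48 eyes, 11.8% | 72 eyes, 16.7% |

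For the last cell: 600 × 0.4 × 0.3 = 72, and 0.12 / (0.60 + 0.12) = 16.7%. If every missed eye shows CNV on a later FA and is scored as new, and the true incidence is r, the table shows c + (1 − c)·r. The excess is c·(1 − r), which cannot exceed c. The percentages are therefore ceilings on false incidence.

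**Study-eye breakdown, using the Phase 2 counts.** Of the 25 cases, 25 − 17 = 8 had no fellow-eye history. The true risk in the No group is 8 / [165(1 − p)]. The displayed risk is (8 + 17m) / [165(1 − p) + 165·p·m], if missed subjects carry the same risk as other subjects with fellow-eye CNV.

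- p = 20%: true 8/132 = 6.1%; displayed 9.7/135.3 = 7.2% at m = 10% and 13.1/141.9 = 9.2% at m = 30%.
- p = 40%: true 8/99 = 8.1%; displayed 9.7/105.6 = 9.2% at m = 10% and 13.1/118.8 = 11.0% at m = 30%.

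The risk in the Yes group does not change in expectation: 17/33 = 52% at p = 20% and 17/66 = 26% at p = 40%. The contrast therefore shrinks. At p = 40% and m = 30%, the risk ratio falls from 25.8/8.1 = 3.2 to 25.8/11.0 = 2.3. At m = 0 nothing changes.

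**Primary comparison.** History is taken at screening, before randomization, so the error should not depend on arm. A mismeasured baseline covariate then costs a little precision and does not bias the treatment contrast.

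**The case against.** A reader might infer that every fellow-eye CNV older than five years is classed as absent. The documents do not support that. Section 9.2 takes in chronic and ongoing conditions, and CNV that was active or treated within the window is recorded anyway. Randomization also needs a yes/no entry on fellow-eye CNV, with no time limit stated (Protocol 7.1), and SAP 5.2 tabulates it beside the actual status, so disagreement would show in aggregate. SAP 7.4 also sends relevant findings of the baseline physical examination, which covers the eyes (Protocol 9.5), to the medical history. These points narrow the gap but do not close it. Section 9.3 omits the chronic-conditions wording, the source of the randomization entry is not stated, SAP 7.4 does not mention FA or SD-OCT, and the filters use history only.

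A reader might also infer that the trial's CNV safety endpoint is compromised. It is not. That endpoint concerns the study eye, where exclusion 3 bars "Any history or active CNV, associated with AMD or any other cause" with no time limit, on reading-center SD-OCT and/or FA. Because that criterion applies to the study eye, it also does not show that the protocol intended a lifetime look-back for the fellow eye.

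For exudative AMD events, SAP 7.1 requires onset, or worsening in severity, on or after first dose, so an old inactive lesion does not qualify by itself. That stands, and it leaves the FA table as the more exposed of the two fellow-eye analyses. It can be argued that new and first emergence already imply a clean screening FA. That is a reasonable intention, but SAP 7.7 writes the at-risk condition in terms of history and states no baseline-FA condition.

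**Conclusion.** The point holds as a gap in definition with limited reach. Some fellow-eye CNV may be classed as absent, either because it is more than five years old, untreated since and not listed as ongoing, or because it is first seen at screening imaging. The outputs affected are the fellow-eye FA incidence, the study-eye exudative AMD breakdown by fellow-eye status, the fellow-eye CNV subgroup and, to a lesser degree, the fellow-eye GA comparison set. The study-eye endpoint is protected and the primary result is little affected.

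The size cannot be established from the documents. The range in the table rests on assumed p and m, and its upper end also needs every missed eye to be scored as incident, so it should not be read as an estimate. The Phase 2 illustration further assumes equal risk in missed and recorded subjects; at p = 20% it implies a 52% risk in treated subjects with fellow-eye CNV, which suggests caution at that end. The change is worth making because it is cheap and the split by fellow-eye status is where a known risk factor will be read.

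**What to change.** In SAP 5.2, define baseline fellow-eye CNV as CNV in the medical history or CNV on the screening FA or SD-OCT as read by the reading center, using the criteria that SAP 7.7 already gives for reading-center confirmed CNV (a CNV type on FA, or CNV thickness on SD-OCT). Apply this one definition in SAP 6, 6.2.5, 6.6.3, 7.1.1 and 7.7, and state in 7.7 that CNV present on the screening FA is never counted as new. The cost is one extra derivation; the images of both eyes are already scheduled and sent to the reading center.

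Where still feasible, record fellow-eye CNV or neovascular AMD without the five-year limit. This costs more, because it means queries for subjects already enrolled at about 100 sites, and the main correction does not depend on it. Queries could be confined to subjects whose randomization entry says Yes and whose history says No.

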### **9.4. Vital Signs**

Vital signs consist of body temperature, respiratory rate, blood pressure (systolic and diastolic), and heart rate measurements.

On injection visits, vital signs will be measured prior to dosing. Vital signs should be taken with the patient in a seated position after resting for 5 minutes. Vital signs will be measured before venipuncture.

### **9.5. Physical Examination**

A physical exam will be performed and should include but should not be limited to an evaluation of the eyes, ears, nose, throat, lymph nodes, head, and neurological function. A patient's height and weight should also be measured at screening. If any abnormalities are noted at screening, the PI, or designee, should determine the clinical significance of the finding and whether this will pose any safety risk to the subject. Any changes from baseline should be noted and the clinical significance assessed. Any new, clinically significant, findings should be documented as AEs.

